#### ***3.1. Duration of Study***

Phase 1: Participants will be asked to complete a one-time interview lasting approximately 60 minutes.

Phase 2: Participants will be asked to complete the intervention over a period of 6 weeks. Participants will be asked to complete 6-week online self-management educational modules and 6 weekly peer mentor calls to facilitate engagement with the online modules and offer specialized support.

Phase 3A: Usability sessions will last approximately 1-hour. Given that usability testing is iterative and design changes are made in response to participant feedback, we will ask some participants if they are willing to review the product another time after changes are made, up to a total of five times. Each session is voluntary and conducted in a way to minimize participant burden.

Phase 3B: Participants assigned to the intervention will be asked to complete it over a period of approximately 8 weeks (which includes 6 peer mentor calls and five corresponding online modules). All participants will be asked to complete surveys at four time points: baseline, immediate post-intervention (~8 weeks after baseline), 3-month follow-up (~5 months after baseline), and 9-month follow-up (~12 months after baseline).

### **3.2 Study Sites**

Phase 1 & 3a: Interviews will be conducted at the Rutgers Cancer Institute of New Jersey or via phone.

Phase 2&3b: Peer mentors will be trained at the Rutgers Cancer Institute of New Jersey or via phone or online webinars. Participants will receive intervention materials online, via email, or via text messaging.

### **3.3 Sample Size Justification**

Phase 1: Total sample size is 24-28, including 10 AYA survivors, 10 parents of AYA survivors, and 4-8 physicians who work with AYA survivors. Qualitative data will be analyzed on a continuing basis. Pooling data across participants, we expect 24-28 interviews will be adequate to achieve data saturation (that is, no new themes emerge from additional participants).

Phase 2: 40 AYA survivors and 20 peer mentors will be recruited for the pilot trial to evaluate feasibility (primary objective) and preliminary outcomes (secondary objective). As this is a feasibility study, we recognize we are underpowered to detect small or medium effects. Published data suggest 5-9% of survivors are African American or Hispanic; data from the NJSCR show greater diversity, with 11.6% of patients diagnosed with cancer at age 10-19 during the period of 2008-2012 reporting as African American, 19% reporting as Hispanic, and 5.7% as Asian American/Pacific Islander. We will oversample these groups.

Phase 3A: Up to 20 AYA survivors will be recruited for usability testing of the online intervention. Given the preliminary work conducted in Phase 2, we expect 12-20 sessions will achieve data saturation (i.e., no new issues emerge according to pre-specified stopping criteria). Usability testing is designed to be iterative in that changes can be made to the site after a small number of participants. Therefore, participants who agree may be asked to complete multiple usability sessions over the course of a few months to provide additional feedback on changes or new features added. Thus we expect about 12 to 20 participants will be needed to achieve data saturation.

Phase 3B: Total sample size is 50 AYA survivors. We chose the sample size and decision rules so that the probability of declaring feasibility would be approximately 5% under unacceptable rates of acceptance/completion and exceed 95% under acceptable rates. If true acceptance and completion rates were 41% and 70%, respectively, which we consider too low to move to an efficacy trial, then the probability of declaring feasibility would be 5%.

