**Table 1. Feasibility decision rules.**

Feasibility	Unacceptable Rate	Acceptable Rate	Decision rule for claiming Feasibility	Prob. Declare Feasible under Unacceptable Rates	Prob. Declare Feasible under Acceptable Rates
Acceptance	41%	50%	If 50 recruited by the 100th eligible	5%	97%
Retention	70%	80%	40 people complete	5%	94%

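### Section 3.3 claims about 5% and over 95% for declaring feasibility in Phase 3B, but no rule combines the two Table 1 criteria and no plausible reading delivers both figures

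*Combined protocol and SAP*

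**What the plan says.** For Phase 3B, Section 3.3 fixes the size ("Total sample size is 50 AYA survivors") and says that this size and the decision rules were chosen so that the chance of a feasibility declaration would be "approximately 5% under unacceptable rates of acceptance/completion and exceed 95% under acceptable rates". It then describes one scenario, "If true acceptance and completion rates were 41% and 70%, respectively", and gives it one probability: "which we consider too low to move to an efficacy trial, then the probability of declaring feasibility would be 5" per cent.

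Table 1 in the same section sets out two rules. Each has its own probability at the unacceptable and the acceptable rate:

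- Acceptance (41% against 50%): "If 50 recruited by the 100th eligible"; 5% and 97%.
- Retention (70% against 80%): 40 people complete follow-up; 5% and 94%.

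Neither Section 3.3 nor the Phase 3B analysis text in Section 5 says whether feasibility needs both rules to be met or only one. Section 5 lists enrollment, retention and intervention completion as separate hypotheses to be examined descriptively. Section 1.1 (Aim 2, Hypothesis 1) joins the enrollment and retention expectations with 'and', but states them as what the team expects and not as a decision rule.

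**The concern.** The text gives a single pair of probabilities for declaring feasibility, while the table holds two rules with two pairs. Two rules can be combined in more than one way, and the overall probabilities depend on which way is chosen.

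Two things are at stake. The pair is the stated reason for 50 participants, and Section 3.3 links the low rates to whether an efficacy trial should follow. If the pair does not describe the rule that is used, the decision lacks the properties claimed for it. Also, a split result, with one criterion met and one missed, has no defined outcome, so it would have to be judged after the data are seen.

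**Working it through.** **Inputs.** From Table 1: acceptance 0.05 and 0.97, retention 0.05 and 0.94. The rules are read as at least 50 of the first 100 eligible, and at least 40 of the 50 enrolled. The 'completion' rate in the Section 3.3 text is taken to be the retention row, because both use 70%.

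**1. The plan's pair from its own printed entries, assuming independence.**

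- Both required: 0.05 × 0.05 = 0.0025 (0.25%), and 0.97 × 0.94 = 0.9118 (91.2%).
- Either enough: 1 − 0.95 × 0.95 = 0.0975 (9.75%), and 1 − 0.03 × 0.06 = 0.9982 (99.8%).

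The first reading misses both targets. The second meets the 95% target but nearly doubles the 5%.

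**2. Read row by row, with no combination.** The 5% agrees with both rows. Acceptance at 97% is above 95%; retention at 94% is not.

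**3. Dropping independence.**

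- Both required: at acceptable rates the joint probability lies between 0.97 + 0.94 − 1 = 91% and min(0.97, 0.94) = 94%. It cannot exceed 95%. At unacceptable rates it lies between 0 and 5%.
- Either enough: between 5% and 10% at unacceptable rates, and between 97% and 100% at acceptable rates. The claimed pair appears only at the extreme of perfect positive dependence (5% / 97%).

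**4. Only one rate unacceptable, both criteria required, printed entries, independence.**

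- Acceptance unacceptable: 0.05 × 0.94 = 4.7%.
- Retention unacceptable: 0.97 × 0.05 = 4.85%.

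On the printed figures, 5% is therefore an upper bound on false declaration under a 'both' rule. It is not the probability in the scenario the text describes, where both rates are unacceptable.

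**5. Table 1 entries recomputed from their own rules (exact binomial).**

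| Criterion | At unacceptable rate | At acceptable rate |
|---|---|---|
| Acceptance, P(X ≥ 50), n = 100 | 4.3% (printed 5%) | 54.0% (printed 97%) |
| Retention, P(X ≥ 40), n = 50 | 7.9% (printed 5%) | 58.4% (printed 94%) |

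Strict inequalities (more than 50, more than 40) do not recover the printed values: acceptance becomes 2.7% / 46.0% and retention 4.0% / 44.4%.

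**6. Combining the exact entries, assuming independence.**

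- Both required: 0.0428 × 0.0789 = 0.34%, and 0.5398 × 0.5836 = 31.5%.
- Either enough: 1 − 0.9572 × 0.9211 = 11.8%, and 1 − 0.4602 × 0.4164 = 80.8%.
- Both required, one rate unacceptable: at most 4.3% if it is acceptance and at most 7.9% if it is retention, since a joint probability cannot exceed either component.

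**7. How often the result would be split at acceptable rates.** The 'either' probability minus the 'both' probability is 99.8 − 91.2 = 8.6% on the printed entries and 80.8 − 31.5 = 49.3% on the exact ones.

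**The case against.** The strongest defence is that the text only summarises Table 1 row by row. It pairs the two rates with 'respectively', and the table that follows gives each criterion its own probability of declaring feasibility. On that reading the 5% is right as printed and the only numerical mismatch is one point, 94% against a figure said to be above 95%. This reading is available, so it cannot be taken as settled that the plan meant one overall probability. It still leaves the retention mismatch and the undefined split result.

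The objection has three further parts.

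- A reader might infer that no combination whatever could give the claimed pair. That goes too far: step 3 shows one exception, an 'either' rule with perfect positive dependence. It is not credible, because with the true rates fixed there is no evident reason why the number accepting should determine how many of the 50 enrolled complete.
- A reader might infer that the 5% is simply wrong if both criteria are required. On the printed entries it holds as a conservative upper bound; the half of the claim that fails is the one above 95%.
- The plan is not wholly silent. The wording of Hypothesis 1 points towards requiring both, although it is an expectation and sets no decision.

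It is also fair to say that the practical consequence is limited. This is a 50-person pilot with descriptive feasibility analyses, and no later phase in this protocol is formally gated on Table 1.

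**Conclusion.** The point stands as a missing combining rule together with a stated pair of probabilities that no plausible reading delivers. On the printed entries the discrepancy is moderate: 0.25% / 91.2% if both are required, 9.75% / 99.8% if either is enough, and a one-point miss for retention if the rows are read separately. For a 'both' rule the failure of the 95% claim needs no independence assumption.

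A reader might attribute the fall to 31.5% to the missing rule. The figures do not support that. Under the same 'both' rule, replacing the printed entries with the exact ones moves the result from 91.2% to 31.5%. The main cause is that 97% and 94% do not follow from the stated cut-offs, which is a separate defect. Adding a combining rule alone would not restore the claimed probabilities.

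The products and the 'either' figures assume that the two counts are independent given the true rates. The retention figures also assume that exactly 50 are enrolled, whether or not the acceptance rule is met.

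**What to change.** Make one change to Section 3.3, together with the correction of the Table 1 entries.

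- State how the two criteria combine, and so what a split result means. The choice is the study team's; requiring both fits Hypothesis 1.
- Say whether the third feasibility hypothesis, more than 75% of modules and mentor calls completed, is part of the decision or only descriptive. It has no row in Table 1.
- Replace the sentences giving 5% and above 95% with the joint probabilities. If both criteria are required and the cut-offs stay at 50 of 100 and 40 of 50, these are about 0.3% when both rates are unacceptable; at most 4.3% when only acceptance is unacceptable and at most 7.9% when only retention is; and about 31.5% when both are acceptable. State the independence assumption. If correcting Table 1 leads to different cut-offs, recompute all of these.

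The drafting cost is a few sentences and an extra table row for the joint rule. Stating the rule and the correct probabilities does not by itself change the sample size or procedures. The real cost is that the stated probability of declaring feasibility at acceptable rates becomes much less favourable, and the team may then wish to reconsider the cut-offs or the rates.

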**Table 1. Feasibility decision rules.**

Feasibility	Unacceptable Rate	Acceptable Rate	Decision rule for claiming Feasibility	Prob. Declare Feasible under Unacceptable Rates	Prob. Declare Feasible under Acceptable Rates
Acceptance	41%	50%	If 50 recruited by the 100th eligible	5%	97%
Retention	70%	80%	40 people complete	5%	94%

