### **Aim 2: Evaluate the feasibility of the self-management + peer mentoring program.**

We will examine feasibility through study enrollment rates, retention rates, adherence to the intervention, reasons for study drop out, and patient and mentor satisfaction with the program.

*Hypothesis 1:* Based on literature, we expect enrollment >50% of eligible patients and retention >80%.

*Hypothesis 2:* We expect patients enrolled in the mentor program to complete >75% of intervention sessions

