## Promoting Follow-Up Care Self-Management for Adolescent and Young Adult (AYA) Childhood Cancer Survivors

[name], MPH

ion			the follow-up		
-----	--	--	---------------	--	--

Sample size was based on the primary feasibility aim, but we also calculated detectable group difference in the primary outcome of the RTQ Adolescent Responsibility total score at the 6-week post-intervention time. Based on survey data, we expect AYA survivors to score an average of 2.57 ( $SD = 0.83$ ) at baseline. Using an independent t-test assuming the control group remains at baseline levels and two-sided alpha of .05, we have 80% power to detect a group difference of 0.66 in the outcome. This would represent the intervention group increasing from “sometimes” to “often” being responsible, which we consider clinically meaningful.

Up to 20 mentors will participate. Mentors will be matched 1:1 with AYA survivors; each mentor may agree to work with up to 5 individuals. As in Phase 2, we expect that several mentors will choose to mentor more than one individual, so a sample size of up to 20 is reasonable.

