### Phase 3B:

**Data Management:** The same procedures used in Phase 2 will be used in Phase 3B, with the exception that TigerConnect (previously called TigerText) will be used for secure messaging as well as secure videoconferencing (instead of doxy.me). Additionally, TigerConnect now allows for secure file transfer so that peer mentors can securely transfer audio recordings to the study team either via Rutgers LiFT or TigerConnect. For participants who consent to be contacted for future studies, the study team will store their contact information separately from research records on the PI's secure One Drive, with access granted only to the PI, study coordinator, and limited authorized research staff. We will store this information for up to 10 years from date of consent.

We will utilize HIPAA compliant Qualtrics survey tool to request the name and contact information of the physician they have seen in the past 12 months to understand their health care utilization during the study period and to obtain their electronic signature on the Release of Medical Record form. Any paper copies will be kept in a locked filing cabinet in the PI's office.

**Data Analysis:** We will examine feasibility through study enrollment rates, retention rates, usability/engagement with online modules and peer mentor, barriers to engagement, and reasons for study drop out. Descriptive analyses (frequencies, means, confidence intervals) will be used to evaluate hypotheses regarding enrollment ( $>50\%$ ), retention ( $>80\%$  complete all surveys), and intervention completion ( $>75\%$  modules/mentor calls). Multilevel modeling (MLM) will be used to examine differences between the intervention and usual care groups over time on transition readiness (RTQ Adolescent Responsibility and TRI total scores). Our primary analysis will consider both time and treatment to be categorical with an interaction between the two. The interaction will be assessed to determine whether change in transition readiness differs between the two groups. The MLM approach assumes any missing observations are missing at random but includes all observed data. Exploratory analyses of additional outcomes (e.g., self-efficacy, adherence to medical appointments and screenings, and health behaviors) will use the identity link or the logit link as appropriate for continuous or binary outcomes.

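### Table 1 overstates the chance of declaring feasibility at the acceptable rates: its own rules give 54% and 58%, not 97% and 94%

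*Combined protocol and SAP*

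**What the plan says.** Section 3.3 fixes the size of the randomised phase: "Phase 3B: Total sample size is 50 AYA survivors". It says that size and rules were chosen so that "the probability of declaring feasibility would be approximately 5% under unacceptable rates of acceptance/completion and exceed 95% under acceptable rates". After Table 1 it adds: "Sample size was based on the primary feasibility aim".

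Table 1 gives two rules:

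| | Unacceptable rate | Acceptable rate | Rule | Stated pass probability, unacceptable | Stated pass probability, acceptable |
|---|---|---|---|---|---|
| Acceptance | 41% | 50% | "If 50 recruited by the 100th eligible" | 5% | 97% |
| Retention | 70% | 80% | "40 people complete" (the follow-up) | 5% | 94% |

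The same thresholds appear elsewhere as strict inequalities. Hypothesis 1 under Aim 2 (section 1.1) reads "we expect enrollment >50% of eligible patients and retention >80" per cent. The Phase 3B data analysis in section 5 sets retention at more than 80% who "complete all surveys".

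**The concern.** A rule whose cutoff sits at the expected count passes about half the time when the true rate is the one that defines the cutoff. Fifty of 100 is exactly 50%, and 40 of 50 is exactly 80%. Pass probabilities of 97% and 94% at those rates therefore cannot be right, whatever method was used. Table 1 also conflicts with the text beside it, which promises more than 95% while the retention row prints 94%.

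These figures are the stated reason for N = 50, and section 3.3 links the rules to whether an efficacy trial should follow. A reader who believes 97% and 94% will take a missed rule as strong evidence that the programme is not feasible. With the true probabilities, a miss is almost as likely as a pass for a programme at exactly the rate the plan calls acceptable.

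**Working it through.** **Inputs.** Acceptance: n = 100 eligible, cutoff 50, rates 41% and 50% (Table 1). Retention: cutoff 40, rates 70% and 80% (Table 1); n = 50 is the Phase 3B total in section 3.3, since Table 1 prints no denominator.

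**Formula.** P(pass) = P(X ≥ k), with X binomial(n, p). For acceptance, having the 50th recruit by the 100th eligible patient is the same event as at least 50 acceptances in 100; the negative binomial form gives the same 0.5398.

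**1. The plan's own figures.**

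| Rule | True rate | Stated | Exact |
|---|---|---|---|
| ≥50 of 100 | 41% | 5% | 4.3% |
| ≥50 of 100 | 50% | 97% | 54.0% |
| ≥40 of 50 | 70% | 5% | 7.9% |
| ≥40 of 50 | 80% | 94% | 58.4% |

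Only the acceptance figure at 41% is about right. The normal approximation at the acceptable rates gives 50.0% for both rules without continuity correction, and 54.0% and 57.0% with it, so the choice of method does not explain the gap.

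**2. Chance of a wrong miss at the acceptable rate.** Acceptance: 100 − 54.0 = 46.0% (implied by the plan: 100 − 97 = 3%). Retention: 100 − 58.4 = 41.6% (implied: 100 − 94 = 6%).

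**3. Strict reading of the thresholds.** If retention must exceed 80%, the cutoff is 41 of 50: 4.0% at a true 70% and 44.4% at a true 80%. If acceptance must exceed 50% with recruitment capped at 50, the 50th recruit must come by the 99th eligible patient: 3.5% at 41% and 50.0% at 50%. Neither moves towards the stated values.

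**4. Can another cutoff rescue the claim?**
- n = 100: at least 95% at a true 50% needs a cutoff of 42 or lower (42 gives 95.6%, 43 gives 93.3%). A cutoff of 42 passes a true 41% with probability 45.7%.
- n = 50: at least 95% at a true 80% needs 35 or lower (35 gives 96.9%, 36 gives 93.9%). A cutoff of 35 passes a true 70% with probability 56.9%.

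**5. Can another denominator rescue it?** With the cutoff of 40 completers, 49 enrolled gives 4.8% at 70% but only 47.2% at 80%; 56 enrolled gives 95.7% at 80% but 47.3% at 70%. With 50 recruits, 117 eligible gives 95.2% at 50% but 38.5% at 41%. No denominator tried gives both properties. For scale, the smallest single-stage designs with at most 5.5% at the lower rate and at least 95% at the upper need about 325 eligible (41% against 50%) and about 200 enrolled (70% against 80%).

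**6. Where do the stated rules reach 95%?** Solving P(pass) = 0.95 for the true rate gives 57.7% for 50 of 100, 87.1% for 40 of 50, and 88.7% for 41 of 50.

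**7. Possible origin.** P(X ≥ 41 of 100 at 50%) = 97.2% and P(X ≥ 36 of 50 at 80%) = 93.9%, which match the printed figures. Those are the chances of reaching, or just exceeding, the unacceptable rate. This is inference; the plan does not show its calculation, and the finding does not depend on it.

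**The case against.** The arithmetic is not open to dispute: the page break inside Table 1 splits words, not numbers. The serious objections concern scope and remedy.

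- *The error may lie in the rates rather than the probabilities.* With the cutoffs as written, 97% and 94% arise at true rates of about 58.8% and 86.7%. The 50% and 80% could have been meant as thresholds to be exceeded, not as assumed true rates. This is possible, but nothing in the plan says so, and Table 1 labels them as the acceptable rates. The sponsor should confirm.
- *The conflict between the two retention wordings is small.* Hypothesis 1 is an expectation and section 5 describes descriptive analysis; only Table 1 calls its criterion a decision rule. That is fair, but exactly 40 completers of 50 would satisfy Table 1 and fail the section 5 hypothesis, and that one participant moves the pass probability at 70% from 7.9% to 4.0%, across the 5% target.
- *Correcting the figures leaves N = 50 without its stated justification.* True. It is a cost of the correction, not a reason to keep the figures.
- *Other details stay open.* Section 3.3 refers to a single probability of feasibility without saying whether both rules must pass. If both must and they are independent, it is about 32% at the acceptable rates (0.540 × 0.584) and 0.3% at the unacceptable rates. Table 1 counts completion of the follow-up, while section 5 counts completion of all surveys. Both points are worth settling, and neither affects the result above.
- *This is a minimal-risk pilot that need not be highly powered.* Agreed, but the plan claims specific operating characteristics and bases its sample size on them.

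**Conclusion.** The concern holds. At the acceptable rates the rules pass 54.0% of the time for acceptance and 58.4% for retention, which is 43 and 36 percentage points below the figures in Table 1. The promise in section 3.3 of more than 95% is not met, and no cutoff at 100 eligible or 50 enrolled meets it while keeping the lower-rate probability near 5%. The retention figure at the unacceptable rate is also off: 7.9% under Table 1's wording, against a stated 5%.

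The result assumes independent participants with a common rate and a retention denominator of the 50 enrolled. The acceptance result uses only figures printed in Table 1. Because these figures are the stated basis for the sample size, they must be corrected.

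**What to change.** Keep N = 50 and the cutoffs, and correct the figures:

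1. Restate the two probability columns of Table 1 as 4% and 54% for acceptance and 8% and 58% for retention. If the retention rule is to be more than 80% (41 or more), its row becomes 4% and 44%.
2. In section 3.3, remove the claim of more than 95% at the acceptable rates and the closing claim of 5%. Suggested replacement: *The chance of meeting each rule is about 4% (acceptance) and 8% (retention) if the true rates are 41% and 70%, and about 54% and 58% if they are 50% and 80%. It reaches about 95% at true rates of about 58% and 87%.* If the rule is 41 or more, the retention figures in that text become 4%, 44% and 89%.
3. State the retention rule once, as 40 or more or as more than 80%, with its denominator of 50 enrolled, and use that wording in Table 1, Hypothesis 1 and the Phase 3B analysis in section 5. The same edit can say which assessment counts as completion and whether both rules must pass.

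If the sponsor finds that the acceptable rates, not the probabilities, were misprinted, those should be corrected and the probabilities recomputed from them.

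**Cost.** Wording only: no extra participants, and no change to the rules unless the sponsor settles on 41 for retention. The downside is that the operating characteristics will look clearly less favourable, and N = 50 can no longer be defended as a 5%/95% design.

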**Phase 3B:**

Peer mentor eligibility includes:

- (1) age 21-29
- (2) at least 2 years from treatment
- (3) self-reported primary responsibility for care and “complete readiness” to assume responsibility for care or high scores (3 or 4) on all items from the Readiness for Transition Questionnaire

Patient eligibility includes:

- (1) age 18-25
- (2) at least 2 years from treatment for any pediatric cancer diagnosed at age 0-19
- (3) currently does not independently self-manage follow-up care according to self-report (i.e., reports parent is primarily responsible or low readiness to assume total responsibility for care [score of 1 or 2 out of 4 on overall readiness item OR scores <3 on two or more items of the 10-item responsibility scale) using the Readiness for Transition Questionnaire)

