Phase 3B: As done in Phase 2, peer mentors will be recruited via advertisements in the CINJ LITE clinic and newsletter, AYA cancer support groups, and online forums/social media, such as stupidcancer.org. Following the Children's Oncology Group's approach to recruiting patient advocates, potential mentors will complete an application including two references or a letter of recommendation. The PI or study staff will interview candidates to evaluate interpersonal skills, level of commitment to the program, and counseling or related experience. Participants for the randomized trial will be recruited using the New Jersey State Cancer Registry (NJSCR). All participant information and surveillance data from the NJSCR is collected and maintained by the NJSCR following Standard Operating Procedures (see IRB#Pro20140000992 NJSCR SEER Data Repository). Patient contact procedures, tracking, and data release also follows NJSCR Standard Operating Procedures. Per Standard Operating Procedures, NJSCR staff will contact the physician of record for eligible cases to notify the physician about the study and that staff will be contacting the patient. An introductory letter and flyer will be mailed to potential participants. NJSCR staff will make follow-up phone calls to provide additional information and, for patients who express interest in participating, to obtain permission to send their contact information to [name] study staff, who will then contact the patient for further details and discussion of consent. NJSCR staff will send second mailings to participants who they are unable to reach via phone, with an informational sheet and an option for participants to respond via mail. At the end of the study NJSCR will provide investigators with aggregate de-identified data (i.e., age, gender, time since diagnosis, etc.) on refusals, so that a comparison can be made between "refusals" and the "acceptors."

To maximize the enrollment, we will also recruit mentors and participants during routine CINJ LITE clinic visits or by mail. We will include an approved study recruitment flyer and study staff will follow-up with a phone call to answer any questions and, if interested, initiate the consent process.

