#### **3.5.4 Consent Procedures**

Phase 1 and 2: The study will be explained to the potential participant by the Principal Investigator or trained study staff via phone. The PI or study staff will review essential elements of consent and answer any questions. Interested and eligible participants will be emailed a link to an online consent form prior to starting the program. To consent, potential participants will be instructed to click "submit the form" button in order to consent.

Phase 3A: The study will be explained to the potential participant by the Principal Investigator or trained study staff in person or on the phone. All subjects will receive a

copy (paper or electronic) of the consent form. To document the process of the consent, we will complete “documentation of Consent Process” form to document that 1) study subjects were provided with a copy of the Consent Forms, 2) all essential elements of informed consent were discussed with subjects, 3) subjects were given adequate time to read and discuss the study with study staff, and 4) all questions asked by the subjects about the study were answered.

Phase 3B: As done in Phase 2, the study will be explained to the potential participant by the Principal Investigator or trained study staff via phone. The PI or study staff will review essential elements of consent and answer any questions. Interested and eligible participants will be emailed a link to an online consent form prior to starting the program. To consent, potential participants will be instructed to click “submit the form” button in order to consent. Since consent forms will be completed online, we are requesting a waiver of documentation of consent.

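### Is Table 1's acceptance rule unsound because it does not say which people make up the 100 eligible?

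*Combined protocol and SAP*

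**What the plan says.** The acceptance row of Table 1 (section 3.3) sets an unacceptable rate of 41%, an acceptable rate of 50%, and the rule "If 50 recruited by the 100th eligible". It prints a 5% chance of passing at the first rate and 97% at the second. Hypothesis 1 (section 1.1) expects more than half of eligible patients to enrol. The Phase 3B analysis in section 5 repeats the 50% figure without naming a denominator and evaluates it descriptively, with confidence intervals.

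The Phase 3B text uses the word eligible at more than one stage:

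- **Before contact (section 3.5.3).** "NJSCR staff will contact the physician of record for eligible cases to notify the physician about the study". Registry staff then telephone and, "for patients who express interest in participating, to obtain permission to send their contact information" to the study team. For those not reached, "NJSCR staff will send second mailings to participants who they are unable to reach via phone".
- **After the study has been explained (section 3.5.4).** "Interested and eligible participants will be emailed a link to an online consent form prior to starting the program".
- **Inclusion criterion 3 (section 3.5.1).** The patient "currently does not independently self-manage follow-up care according to self-report", judged on the Readiness for Transition Questionnaire (RTQ).

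There is also a clinic route: "we will also recruit mentors and participants during routine CINJ LITE clinic visits or by mail". At the end of the study the registry supplies aggregate data on those who declined, for comparison with those who accepted.

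**The concern.** A rule that stops counting at the 100th person depends on who is counted. Registry cases cannot be known to meet criterion 3 before contact. Under section 4.1 the registry provides diagnosis and date of diagnosis, and the rest is self-report. No section describes giving the RTQ to people who decline the registry call or are never reached, so their full eligibility stays unknown. The plan does not say whether they belong in the 100, or how clinic recruits enter it.

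Section 3.3 bases the sample size on the feasibility aim, and acceptance is one of its two decision rules. If the same recruits pass on one count and fail on another, the choice could be made after the numbers are known. Counting only people who were interested enough to be screened could also flatter acceptance. Those possibilities made the point worth checking.

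**Working it through.** **Inputs.** From Table 1: 50 recruits, the 100th eligible person, rates of 41% and 50%. Every eligibility, interest and contact rate below is an assumption, because the documents give none.

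**1. The plan's own figures.** Passing means X ≥ 50 with X ~ Binomial(100, q), where q is the acceptance rate in the counted group.

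- q = 0.41: P = 0.043, in line with the stated 5%.
- q = 0.50: P = 0.540, against the printed 97%. This mismatch is a separate matter. It arises whichever group is counted, so it has no bearing on the choice of denominator.

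Step 1 uses nothing about how the group was formed. The 4.3% holds for any group whose own acceptance rate is 41%.

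**2. Registry cases against confirmed-eligible people.** Let f be the share of registry cases that prove eligible and a the acceptance rate among those. Acceptance per registry case is f × a.

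| f | 50 of 100 confirmed eligible becomes | P(pass on registry count), a = 0.50 |
|---|---|---|
| 0.9 | 50/111 = 45% | 0.18 |
| 0.82 | 50/122 = 41% | 0.043 |
| 0.7 | 50/143 = 35% | 0.0015 |

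The denominator can therefore move the result from one design rate to the other.

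**3. Screened people only, with 41% taken as the rate among all eligible people.** If a share r of eligible people reaches screening, q = 0.41/r. For r = 0.9, 0.8 and 0.7, P(pass) = 0.214, 0.637 and 0.966. The rise comes entirely from the added premise that 41% belongs to the wider group. If 41% belongs to the screened group, P returns to 0.043.

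**4. Decliners of unknown status kept in, known RTQ failures removed.** With e the RTQ-eligible share, r now the share interested, and interest unrelated to RTQ status, q = p·e / (1 − (1 − e)r). Here p is acceptance among all RTQ-eligible people. At p = 0.50, P(pass) runs from 0.057 (e = 0.6, r = 0.7) to 0.443 (e = 0.8, r = 0.9), against 0.540 with eligibility fully known. No section of the plan describes this count; it is one possible construction.

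**5. How often do the counts in steps 3 and 4 disagree?** Take 50 recruits, e = 0.7 and r = 0.8, and vary only the number of registry cases reached. The screened count is N × 0.7 × 0.8. The count in step 4 is N − N × 0.3 × 0.8.

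| Cases reached, N | Screened eligible | Not found ineligible | Result |
|---|---|---|---|
| 130 | 50/73 = 68% | 50/99 = 51% | pass on both |
| 160 | 50/90 = 56% | 50/122 = 41% | pass, fail |
| 200 | 50/112 = 45% | 50/152 = 33% | fail on both |

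Disagreement is possible, but it needs a particular intake. Nothing in the documents says how likely that intake is.

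**6. Do the passages define two rival groups?** Section 3.5.4 names two attributes, interest and eligibility. The second carries its ordinary meaning, the criteria of section 3.5.1 with the exclusions of section 3.5.2; the phrase does not redefine eligible people as interested ones. In section 3.5.3 the word describes cases selected for contact. Only section 3.5.1 sets out criteria, so it is the natural referent for Table 1.

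**The case for a change.** The strongest reply is that reading eligible as meeting section 3.5.1 does not close the gap. People who decline the registry call are never screened, so leaving them out measures consent among people already inclined to take part. The planned comparison of decliners with acceptors suggests that decliners matter to acceptance. Section 3.3 also treats 41% as too low to move to an efficacy trial, so the count has consequences. If 41% was meant for all eligible survivors, step 3 shows a chance of 21% to 97% of passing at that rate.

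Part of this stands. The plan does not state the denominator, nor how decliners, never-reached patients and clinic recruits are counted.

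The rest is weaker. The comparison of decliners with acceptors uses end-of-study aggregates such as age, gender and time since diagnosis. That is a check on representativeness and is poorly suited to feeding a running count to the 100th person. Nothing in section 3.3 attaches 41% to a population wider than the one counted. The Standard Operating Procedures that govern registry contact and tracking are not among the documents, so their silence on dispositions proves little. Settling the count after seeing the numbers is possible, but nothing in the plan points to it.

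**Conclusion.** No change follows. The omission is real, but it is missing detail and not a wrong rule. People found to meet section 3.5.1 can be counted in order of screening. A recruitment and tracking database is planned in section 5 for Phase 2, and its procedures carry over to Phase 3B. On that count the rule has the stated error of about 5% (4.3% exactly) when the group's own acceptance rate is 41%. A wider count of everyone offered the study would also be defensible, but it answers a different question and would not correct an error in the first.

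The size of any distortion cannot be fixed from the documents. The pass probabilities in steps 2 to 4 and the example in step 5 are illustrations under assumed rates, and those in steps 3 and 4 also require the design rates to refer to all RTQ-eligible people. In a feasibility pilot whose enrolment is reported descriptively with confidence intervals, analysts would ordinarily state who was counted and show the flow from registry and clinic to consent. A reader could then judge the 50% figure on either denominator.
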